#### **Treatment Plan (Phase II and Exploratory Cohort)**

Patients will be treated with oral 5-azacytidine and romidepsin at the MTD (i.e the Recommended Phase 2 Dose, or RP2D). The treatment will be administered as follows: oral 5-azacytidine 300 mg (flat dose) Days 1-14 and romidepsin 14 mg/m^2 on Days 8, 15, and 22 on an every 35 day cycle. .

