#### 5.1.6 Dose De-escalation Decision Rules:

If a DLT is reached in the first cycle for a given patient, then the previous dose level will be utilized for that particular patient in subsequent cycles. Should that patient experience a second DLT at that lower dose, they will be removed from the study. Dose-escalation will resume until the maximally administered dose is achieved or MTD is reached.

For example, according to the schema in Table 2, if DLT is reached at dose level 1 (romidepsin 10 mg/m^2 and oral 5-azacitidine 100 mg/m^2), the frequency of romidepsin will be reduced to a Day 8 only dose. Dose escalation can resume starting at that point according to dose escalation rules (Table 3). The same

applies if DLT is reached at all other levels prior to dose level four.

Toxicities in cycles 2 and following may be accommodated by treating patients at one dose level below the present cohort. Toxicity in cycles 2 and beyond will not affect dose escalation for future patients.

In the Phase 2, de-escalation should follow the Phase 1 escalation guidelines. For instance, any recurrent Grade 3 toxicity, up to 3 de-escalations will be allowed, with the doses of the drugs being reduced to that described in Cohort 5 (azacytidine 300 mg Day 1-14, and romidepsin 14 mg/m^2 Day 8 and 15 every 28 days) → Cohort 4 (azacytidine 300 mg Day 1-14, and romidepsin 10 mg/m^2 Day 8 and 15 every 28 days) and then Cohort 3 (azacytidine 200 mg Day 1-14, and romidepsin 10 mg/m^2 Day 8 and 15 every 28 days). Any patient experiencing a Grade 4 toxicity should just be immediately dose reduced according to the guideline above. In addition, patients can be dose reduced per the treating physicians discretion.

Specifically, for hematologic toxicities, patients may receive GCSF for neutropenia. For cases where patients miss a dose secondary to a recurrent Grade 3 ANC or platelet count, or Grade 4 hematologic toxicity, dose reductions should occur as noted above at the physicians discretion (i.e. reduce to Cohort 5, then 4 then 3).

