## **5.5 Duration of Follow Up**

Patients will have an end of study visit 4 weeks +/- 5 days after their last dose of drug to evaluate safety. Patients will be further followed every three months after the 4-week safety evaluation for one year, or until they begin a new treatment for their disease, for evaluation of delayed toxicity. Patients removed from study for unacceptable adverse events will be followed until resolution or stabilization of the adverse event.

For patients who have stable disease or better after 6 cycles of therapy, tumor assessment will be performed by medical history, physical, CBC with differential and chemistries every 3 months until progression of disease occurs. CT (PET/CT optional) will not be routinely used to monitor complete responses after 6 months, but rather, will be used when indicated, due to concern for disease progression.

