# **6. DOSING DELAYS/DOSE MODIFICATIONS**

## **6.1 Dose Delays**

- Study drugs can be administered within 48 hours of their scheduled time.
- Study drugs will be held for DLTs until adverse event returns to  $\leq$  Grade 2
- If interruption lasts for more than 14 days, study treatment will be discontinued.

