**TABLE 8: Dose Modifications for Romidepsin**

Dose Modifications for Romidepsin	
CTCAE Grade or Abnormal Value	Romidepsin
Thrombocytopenia	
Grade 1 ( $75 \times 10^9/L - < LLN$ ) Grade 2 ( $50 - < 75 \times 10^9/L$ )	Maintain dose level Maintain dose level
Grade 3 or 4 thrombocytopenia:  OR  Thrombocytopenia that requires platelet transfusion or recurrent Grade 3 or 4 thrombocytopenia	Hold subsequent doses of therapy until thrombocytopenia returns to $\leq$ Grade 2 or baseline and continue at full dose  Hold subsequent doses of therapy until thrombocytopenia returns to $\leq$ Grade 2 or baseline and permanently reduce dose of romidepsin to the next reduced level below.. If the same toxicity recurs despite dose reduction, patients should be taken off study.
Neutropenia (ANC)	
Grade 1 ( $1.5 \times 10^9/L - < LLN$ ) Grade 2 ( $1.0 - < 1.5 \times 10^9/L$ )	Maintain dose level Maintain dose level
Grade 3 and 4 neutropenia:	Hold subsequent doses of therapy until specific cytopenia returns to $\leq$ Grade 1 or baseline and continue at full dose
Febrile Neutropenia	
Febrile ( $\geq 38.5^{\circ}C$ ) Grade 4 neutropenia or recurrent Grade 3 or 4 neutropenia:	Hold subsequent doses of therapy until neutropenia returns to $\leq$ Grade 1 or baseline and permanently reduce dose of romidepsin to the next reduced level below.. If the same toxicity recurs despite dose reduction, patients should be taken off study
All Other Non-Hematologic Drug Toxicities (not mentioned in previous tables)	
Grade 1 or 2:	Maintain dose level
Grade 3	Hold treatment with romidepsin until toxicity returns to $\leq$ Grade 1 or baseline, then restart therapy at full dose. If Grade 3 toxicity recurs, reduce dose of romidepsin to the next reduced level below.. This is a permanent dose reduction.
Grade 4	Grade 4 toxicity: Hold treatment with romidepsin until toxicity returns to $\leq$ Grade 1 or baseline, and then restart therapy at the next reduced level below.. This is a permanent dose reduction

Dose interruption or study discontinuation is not required for lymphopenia of any grade.

In general, if study drug has been held and the toxicity does not resolve, as defined above, then drug must

be discontinued.

Note: Dose reductions should not be performed for alopecia or for nausea or vomiting that was not treated with aggressive anti-emetic support.

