## 10. STUDY CALENDAR

Baseline evaluations are to be conducted as indicated in the table below, prior to start of protocol therapy. Scans must be done  $\leq$ 4 weeks prior to the start of therapy. In the event that the patient's condition is deteriorating, laboratory evaluations should be repeated within 48 hours prior to initiation of the next

cycle of therapy.

Cycle	Screening	1				2- onward				End of treatment	End of Study (4 weeks after last dose)	Follow-up j
		Day 1	Day 8	Day 15	Day 22	Day 1	Day 8	Day 15	Day 22			
Eligibility & Safety Monitoring												
Informed Consent	X c											
Demographics	X c											
Medical History	X c											
Concurrent Medications	X f	X g	X	X	X	X	X	X	X	X	X	X
Physical exam	X f	X g	X	X	X	X				X	X	X
Vital Signs, weight	X f	X	X	X	X	X				X	X	X
Performance Status	X f	X	X	X	X	X				X	X	X
CBC w/ differential	X f	X g	X	X	X	X	X	X	X	X	X	X
Chemistries a, i	X f	X g				X				X	X	X
EKG	X c		X				X			X	X	
Toxicity Assessment			X	X	X	X				X	X	X
Serum β-hCG	X f											
Urinalysis	X c	X g										
Creatinine clearance	X											
Drug Dispensation												
Oral 5-azacitidine		X				X						
Romidepsin			X	X	X		X	X	X			
Efficacy Measurements												
CT (PET/CT optional)	X c						X b					
Brain MRI	X c, l											
Bone Marrow Biopsy k	X									X c		
Lymph Node Assessment	X c											
PK/Biomarkers												
Lymph Node Biopsy, FNA, or Bone Marrow Biopsy (Optional)	X c		X l									
PK		X d	X d			X						
Correlative Blood Sample		X h										

a) Chemistries include: Chem \*, Mg+, K+, Creatinine, Hepatic Function Panel (LFTs, bilirubin), and LDH. On romidepsin days of cycles 2 and onward, full chemistries may be drawn, but only K+ and Mg+ are required.  
b) CT to occur after cycle 2 and 6, Then CT q3-6 months, until disease progression or initiation of new therapy at the discretion of the Investigator. (PET/CT is optional)  
c) Bone Marrow biopsy will be required after cycle 2 for patients with bone marrow involvement at baseline who have a complete response by imaging and physical exam  

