### 11.2.4

#### Evaluation of Best Response

The best overall response is the best response recorded from the start of the treatment until disease progression/recurrence (taking as reference for progressive disease the smallest measurements recorded since the treatment started). The patient's best response assignment will depend on the achievement of both measurement and confirmation criteria.

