#### **Phase II and Exploratory Cohort**

Primary Objective: To estimate ORR defined as best response by 4 cycles.

Disease and patient characteristics at baseline will be summarized using descriptive statistics. For qualitative variables, frequency distributions and proportions will be provided; for quantitative variables, summary statistics (e.g., mean, median, quartiles, standard deviations, etc) and graphical displays (e.g., box plots). Overall response rates will be estimated upon completion of the study along with exact 95% confidence intervals.

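### Response CTs and the primary ORR window are tied to treatment cycles, so a patient who stops drug early without progression has no dated response scan

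*Combined protocol and SAP*

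**What the plan says.** **ORR window.** Section 13.3 (Phase II and Exploratory Cohort) gives the primary objective as "To estimate ORR defined as best response by 4 cycles". No day or week is attached. Section 11.2.4 defines best response without that limit: "The best overall response is the best response recorded from the start of the treatment until disease progression/recurrence".

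**CT dates.** The Phase II schema puts CT at the end of cycles 2 and 6, then every 3-6 months. Footnote b of the study calendar (Section 10) agrees: "CT to occur after cycle 2 and 6, Then CT q3-6 months, until disease progression or initiation of new therapy", and adds that this is at the investigator's discretion. The opening of Section 11 instead calls for re-evaluation after every even-numbered cycle, which includes cycle 4.

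**Cycle length.** The Phase II regimen is given "on Days 8, 15, and 22 on an every 35 day cycle". The reduced regimens written out in Section 5.1.6 all run "Day 8 and 15 every 28 days".

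**After drug stops.** Section 5.5 describes the three-monthly visits as being for delayed toxicity. Its tumor follow-up is limited: "For patients who have stable disease or better after 6 cycles of therapy, tumor assessment will be performed". The calendar shows no CT at end of treatment, end of study or follow-up.

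**Routes to early stopping.** Section 6.1: "If interruption lasts for more than 14 days, study treatment will be discontinued". The romidepsin dose modification table (Table 8) adds: "If the same toxicity recurs despite dose reduction, patients should be taken off study". Table 7 has similar wording for cardiac findings. Section 5.6 is titled as removal from study, but its text speaks of removal from treatment.

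**Evaluability.** Section 11.1.1 counts a patient as evaluable for response after at least one day of therapy and a disease re-evaluation. Objective progression before the end of cycle 1 is also considered.

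**The concern.** In a single-arm trial with a go/no-go rule on ORR, whether and when a patient is scanned should not depend on how well the drug is tolerated. Here the scans that determine response are dated by cycle number, so a patient who stops for toxicity early in treatment drops off the dated schedule while still free of progression.

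The plan then gives no Phase II rule for such a patient. Counted as a non-responder, a patient whose tumor may have shrunk is scored as a failure. Set aside as not evaluable under Section 11.1.1, the patient leaves a denominator selected for tolerating treatment. The first lowers power and the second inflates the type I error. Both act on a rule with little slack: 9 patients, then 24, with at least 10 responses needed.

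PFS and DOR share the weakness, because the scans that would date progression after an early stop have no fixed dates.

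**Working it through.** **1. Reproduce the design (Section 13.2).** Inputs: null ORR 0.25, alternative 0.50; stage 1 has 9 patients, stopping at 2 or fewer responses; total 24, failing at 9 or fewer.

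P(declare effective | p) = sum over x = 3 to 9 of P(Bin(9, p) = x) × P(Bin(15, p) ≥ 10 − x).

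- p = 0.25: 0.0485 (stated 0.049, a third-decimal difference)
- p = 0.50: 0.805 (stated 80%)
- Early stopping at p = 0.25: P(Bin(9, 0.25) ≤ 2) = 0.601 (stated 0.60)
- Expected size: 9 + (1 − 0.601) × 15 = 14.99 (stated 15)

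The design is sound as stated. The issue is the endpoint fed into it.

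**2. Which dated CTs remain after a stop without progression (schema and calendar).**

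| Drug stopped | Dated CT within 4 cycles | Dated second CT |
|---|---|---|
| Before end of cycle 2 | None | None |
| Between cycles 2 and 6 | End of cycle 2 | None |
| After cycle 6 | End of cycle 2 | End of cycle 6 |

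Even for a patient who stays on drug, this schedule places only one CT inside the ORR window.

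**3. Effect on the decision rule.** Let m be the share of patients with no scan in the window. The documents do not give m, so 5, 10 and 20% are assumptions.

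*Counted as non-responders, assuming they would otherwise respond at 50%.* Observed ORR = 0.50 × (1 − m).

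| m | Observed ORR | Power | Chance of stopping at stage 1 |
|---|---|---|---|
| 0 | 0.500 | 0.805 | 0.090 |
| 5% | 0.475 | 0.737 | 0.117 |
| 10% | 0.450 | 0.656 | 0.150 |
| 20% | 0.400 | 0.470 | 0.232 |

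*Dropped and replaced to reach 24 evaluable, assuming none would have responded and the true ORR in all patients is 25%.* ORR among evaluable = 0.25 / (1 − m).

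| m | ORR among evaluable | Type I error |
|---|---|---|
| 0 | 0.250 | 0.048 |
| 5% | 0.263 | 0.066 |
| 10% | 0.278 | 0.090 |
| 20% | 0.3125 | 0.169 |

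**4. Secondary effect: cycle length.** Reduction after cycle 1 gives one 35-day cycle and then 28-day cycles.

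| End of cycle | Full dose | Reduced after cycle 1 | Shift |
|---|---|---|---|
| 2 | 2 × 35 = day 70 | 35 + 28 = day 63 | 7 days |
| 4 | 4 × 35 = day 140 | 35 + 3 × 28 = day 119 | 21 days |
| 6 | 6 × 35 = day 210 | 35 + 5 × 28 = day 175 | 35 days |

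The stated tolerance for scheduled events is 3 days either way. Under the schema and calendar, the cycle 2 CT stays inside the window and the cycle 6 CT outside it at either cycle length, so ORR is barely affected. The later assessment dates do move.

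**The case against.** The best counter-argument is that CT does not end with drug. The schema and footnote b continue it every 3-6 months until progression or new therapy, and non-progressing patients have three-monthly visits with a physical examination for up to a year or until new treatment. A reader might infer that early stoppers are never imaged again, and the documents do not support that. What remains is that these CTs follow the cycle 6 scan, are discretionary, have no start date for someone who never reaches cycle 6, and sit uneasily with Section 5.5. The missing CT marks in the later calendar columns are weak evidence by themselves, because mark positions there do not match the footnotes. The footnote wording carries the point.

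Four other stronger readings also fail:

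- *Shortened cycles distort ORR.* They move the first CT by at most 7 days. Delays move dates the other way, but Section 5.1.4 says missed doses are not made up, so a hold need not lengthen a cycle.
- *PFS and DOR are censored at a toxicity stop.* Section 13.3 gives no censoring rule for either.
- *The romidepsin PTCL study in Section 7.2.2.4 shows how many responders would be lost.* There, 48 − 34 = 14 of 48 patients (29%) did not receive 2 cycles. The 15 responders are the same in both denominators, so none of the 14 was counted as a responder. Reasons for stopping are not given, and that study was monotherapy.
- *Off study means lost to tumor follow-up.* Section 5.6 speaks of treatment, and Section 5.5 still follows patients removed for adverse events, though until the event resolves or stabilizes. The status is unclear rather than settled.

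Finally, Section 13.2 refers to patients treated in stage 1, which leans toward an all-treated denominator. Section 13.3 states that denominator only for Phase I, and Section 11.1.1 points the other way for response.

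**Conclusion.** The concern holds for early stoppers. No dated response CT covers a patient who stops drug without progression before the end of cycle 2, and no dated second CT covers one who stops between cycles 2 and 6. Because evaluability depends on re-evaluation and Phase II has no stated rule for unscanned patients, ORR can be biased by toxicity in either direction.

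The size depends on an unscanned share that the documents do not supply. At 10%, power would be 0.656 instead of 0.805 under one convention, or type I error 0.090 instead of 0.048 under the other. Both rest on deliberately unfavorable assumptions about how unscanned patients would have responded, so they illustrate sensitivity and are not forecasts. The change in cycle length is secondary: it shifts later assessment dates and hardly touches ORR. The plan should be amended, since the gap bears on the primary endpoint and is cheap to close.

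**What to change.** - Date tumor assessments from Cycle 1 Day 1: day 70, day 140 and day 210, then at the interval already planned. Day 140 is the full-dose equivalent of the cycle 4 re-evaluation that Section 11 already calls for. Without it, no scan would fall between day 70 and the close of the window.
- Close the primary ORR window at the day 140 assessment, including its visit tolerance.
- Keep the same dates for patients who stop drug without progression, until progression or new lymphoma therapy.
- State that all treated patients are in the Phase II ORR denominator.
- Reconcile the schema, Section 5.5, the calendar, the opening of Section 11, Section 11.2.4 and Section 13.3 on scan timing and the ORR window.
- Reconcile the off-study wording in Tables 7 and 8 with the removal-from-treatment wording in Section 5.6, so that tumor follow-up continues. No dosing or stopping rule needs to change for this.

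Cost: amendment wording, with N unchanged at 24. A few early stoppers would have scans that would otherwise lapse. The day 140 CT is an extra scan per patient if the schema and calendar, rather than Section 11, were the intended schedule.

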## **Appendix 1: Medications That May Cause QTc Prolongation**

The following table presents a list of drugs that may prolong the QTc. These drugs are prohibited during the study. Romidepsin may be administered after a 5 half-life washout period elapses following the use of these drugs. Washout period is based on roughly 5 half-lives and rounded to a convenient interval.

## Medications That May Cause QTc Prolongation

Compound (Brand Name)	Compound Half-Life	Possible Washout Period (Hours)	Possible Washout Period (Days)
Antiarrhythmics			
Amiodarone (Cordarone, Pacerone)	58 days (15-142) 36 days (active metabolite)		180
Disopyramide (Norpace, Norpace CR)	6.7 hr (4-10)	36	
Dofetilide (Tikosyn)	10 hr	48	
Flecainide (Tambocor)	20 hr (12-27)		5
Ibutilide (Convert)	6 hr (2-12) (variable among patients)	36	
Procainamide (Pronestyl, Procanbid, Procan)	3-4 hr for PA and NAPA (active metabolite)	24	
Quinidine (Quinaglute, Cardioquin, Quinidex)	6-8 hr in adult; 3-4 hr in children	36	
Sotalol (Betapace, Sorine)	12 hr	72	
Antibiotics			
Clarithromycin (Biaxin, Biaxin XL)	Nonlinear PK 3-4 hr (250 mg Q12) 5-7 hr (500 mg Q12)	36	
Erythromycin (Benzamycin, Eyc, E-glades, Erygel, E-solve 2, Akne-Mycin, Eryderm, Sansac, Erythro-Statin, Erymax, Staticin, T-Stat, C-solve-2, Erycetter, PCE, Ery-Tab, E-Mycin, E-Base, E.E.S., Eryped, E.E.S 200, E.E.S 400, Pediamycin, Eryzole, Erythrocin)	Each salt form has different half-life		
Gatifloxacin (Tequin, Tequin Teqpaq)	7-14 hr	48	
Grepafloxacin (Raxar)	16 hr		3
Antibiotics (cont'd)			
Levofloxacin (Levaquin, Quixin, Elequin)	6-8 hr	48	
Moxifloxacin (Avelox, Vigamox)	12 ± 1.3 hr	72	
Sparfloxacin (Zagam)	20 hr (16-30)		4
Telithromycin (Ketex)	2-3 hr	24	
Anticonvulsants			
Felbamate (Felbatol)	20-23 hr		5
Fosphenytoin (Cerebyx)	12-29 hr		6
Antidepressants			
Venlaflaxine (Effexor)	5 ± 2 hr for parent comp. 11± 2 hr for OVD (active metabolite)	60	
Antidiarrheals			
Octreotide (Sandostatin)	1.7 hr	12	
Antiemetics			
Dolasetron (Anzemet)	8.1 hr		
Droperidol (Inapsin)	2.2 hr	10	
Domperidone (Motilium)	7-8 hr	48	
Palonosetron (Aloxi)	40 hr		10
Antihypertensives			
Moexipril/Hydrochlorothiazide (Uniretic)	2-9 hr(include active metabolite) for moexipril; 5.6-14.8 hr for HCTZ	48	
Antimalarials			
Halofantrine (Halfan)	6-10 days (variable among individuals)		45
Quinidine (Quinaglute, Cardioquin, Quinidex)	6-8 hr in adult; 3-4 hr in children	36	
Antimanics			
Lithium (Eskalith, Lithobid, Lithonate)	24 hr (10-50)		7
Antineoplastics			

Compound (Brand Name)	Compound Half-Life	Possible Washout Period (Hours)	Possible Washout Period (Days)
Arsenic trioxide (Trisenox)	Not characterized		
Tamoxifen (Nolvadex)	5-7 days (biphasic)		30
Antiprotozoals			
Pentamidine (NebuPent, Pentam)	6.4 ± 1.3 hr	36	
Antipsychotic agents			
Chlorpromazine (Thorazine)	30 ± 7 hr		7
Haloperidol (Haldol)	18 ± 5 hr		5
Mesoridazine (Serentil)	24-48 hr (animal study)		10
Pimozide (Orap)	55 hr		14
(Continued from previous page)			
Antipsychotic agents (cont'd)			
Quetiapine (Seroquel)	6 hr	36	
Risperidone (Risperdal, Risperdal Consta)	3-20 hr (extensive to poor metabolizer) 9-hydroxyrisperidone (active metabolite) $T_{1/2} =$ 21-30 hr (extensive to poor metabolizer)		4
Thioridazine (Mellaril)	20-40 hr (Phenothiazines)		7
Ziprasidone (Geodon, Zeldox)	7 hr	36	
Antispasitics			
Tizanidine (Zanaflex)	2.5 hr	12	
Antivirals			
Amantadine (Symadine, Symmetrel)	17 ± hr (10-25)		4
Foscarnet (Foscavir)	87.5 ± 41.8 hr (distribution and release from bone)		20
Analgesics			
Levomethadyl (Orlaam)	Multiple compartment PK with active metabolite 2.6 day for LAAM, 2 day for nor-LAAM, 4 day for dinor-LAAM		20
Asthma medications			
Salmeterol (Advair Diskus, Serevent, Serevent Diskus)	5.5 hr (only one datum)	36	
Calcium channel blockers			
Bepridil (Vascor)	42 hr (26-64)		10
Isradipine (DynaCirc)	8 hr (multiple metabolites)	48	
Nicardipine (Cardene)	~2 hr post IV infusion	12	
Cholinergic enhancers			
Cisapride (Propulsid)	6-12 hr, up to 20 hr	60	
Diuretics			
Indapamide (Lozol)	14 hr (biphasic elimination)		3
Immunosuppressants			
Tacrolimus (Prograf, Protopic)	~34 hr in healthy patients ; ~19 hr in kidney transplant		7
Migraine medications			
Naratriptan (Amerge)	6 hr	36	
Sumatriptan (Imitrex)	2.5 hr	12	
Zolmitriptan (Zomig)	2.8-3.7 hr (higher in female)	18	
Narcotic pain relievers			

Compound (Brand Name)	Compound Half-Life	Possible Washout Period (Hours)	Possible Washout Period (Days)
Methadone (Dolophine, Methadose)	15-30 hr		7
Sedatives			
Chloral hydrate	Readily converted to Trichloroethanol (active metabolite $T_{1/2} = 7-10$ hour)	48	

References:

Physician's Desk Reference 2002

Facts and Comparisons (update to June, 2000)

The Pharmacological Basis of Therapeutics 9th Edition, 1996

## Appendix 2: Medications That May Inhibit CYP3A4

The following table presents a list of drugs that may inhibit CYP3A4. As romidepsin is predominately metabolized by CYP3A4, inhibition of this enzyme could result in elevated plasma levels or increased exposure to romidepsin. Romidepsin may be administered after a 5 half-life washout period elapses following the use of these drugs. Washout period is based on roughly 5 half-lives and rounded to a convenient interval.

